10.3.2 Compliance

Missing data may hamper assessment of HRQoL in clinical trials. This may be because centers do not collect the questionnaires at the appropriate time (unit non-response), and because patients may miss questions within the questionnaires (item non-response). The latter problem occurs less than 2% on average and should not be a problem. The former problem will be minimized by ensuring that participating centers are properly informed and motivated towards HRQoL assessment. During the study, compliance with completing HRQoL questionnaires will be investigated at each time point. The compliance of the HRQoL assessments will also be reviewed twice a year and will be a part of the descriptive report by Data Center for the Group's plenary sessions. The compliance rate between the 2 arms will be compared at each time point using a chi-square test. In order to adjust for the multiplicity of the tests, a Bonferroni adjustment will be made by which each test will be performed at the 0.01 significance level. Should serious volumes of missing questionnaires occur (below 65% at any assessment point) then the protocol writing committee would review the HRQoL assessment in the trial.

Available patient numbers will diminish during the trial due to progression, death, or loss to follow-up. Given the low prognosis of the patient population, the HRQoL assessments appear more frequently early on (first 3 cycles) and only one later follow-up visit is required.

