8.1 Statistical design

8.1.1 Sample size

This trial is a phase II with a Korn superiority design comparing PFS between trabectedin and control with a treatment allocation ratio equal to 2:1 at randomization. Based on RANO recommendation (Ref. 1), PFS-6=15% was assumed in the control arm and 35% in the trabectedin arm (i.e. 20% difference). Assuming PFS follows an exponential distribution, this corresponds to a treatment Hazard Ratio (HR) equal to 0.55. Based on the logrank test, a type I error equal to 10% one-sided (20% two sided), a power equal to 85%, 72 progressions or deaths are needed to assess the targeted effect. 86 eligible patients who started their treatment (per protocol population) should be recruited (57 trabectedin, 29 control). Assuming 7.17 patients per month (1.99 months 0-4, 3.55 months 4-8, 5.29 months 8-12 and 7.17 beyond 12 months), about 18 months of recruitment are needed. Events should be observed shortly (about 3-4 months) after end of accrual.

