10.3 Study design

Patients are eligible for the quality of life assessment in this study if they fulfill the eligibility criteria (Chapter 3) and, complete the baseline HRQoL questionnaire before randomization. Patients will be informed in the written patient informed consent form that they will have to undergo repeated quality of life assessments while involved in this trial. HRQoL will be a secondary endpoint and evaluated in a longitudinal design in all patients entered in this study. HRQoL is a mandatory requirement.

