10.3.1 HRQoL schedule - timing and location

HRQoL questionnaires must be filled out at the hospital when patients come for a scheduled visit according to the EORTC “Guidelines for administration of questionnaires” (see Appendix G). The pre-treatment questionnaires must be filled within 4 weeks prior to randomization. Subsequent questionnaires are filled in as described in the time schedule in this paragraph.

Electronic copies of the HRQoL questionnaires will be sent to the institutions to be printed. Additional translations can be provided to any institution upon request via the EORTC contact person. The case report forms will include a question whether the HRQoL forms have been filled in, and if not, the reason why. The questionnaire will be handed out to the patients by the investigator or a study nurse prior to seeing the doctor for clinical evaluations. The patient should complete the questionnaires by her/himself in her/his own language **prior** to seeing the treating physician at the outpatient clinic as completely and accurately as possible. It is recommended that a key person (e.g. research nurse) at each center should be responsible for questionnaire data collection in order to optimize the compliance of the patient and to ensure the completeness of the data.

During the study, compliance with completing questionnaires will be investigated at each time point. The compliance of the HRQoL assessments will also be reviewed twice a year and will be part of the descriptive report.

The time windows for eligible HRQoL assessments will be as follows:

Assessment	Time window
Baseline	Can be completed before or on the day of start of protocol treatment but no earlier than 28 days before.
Week 3 (End of cycle 1)	To be completed during the third week after treatment start while on protocol treatment. If 3 weekly chemotherapy regimen: can be completed during the third week of the first cycle of chemotherapy (D15-D21 of cycle 1).
Week 6 (End of cycle 2)	To be completed during the sixth week after treatment start while on protocol treatment. If 3 weekly chemotherapy regimen: can be completed during the third week of the second cycle of chemotherapy (D15-D21 of cycle 2).
Week 12 (End of cycle 4)	To be completed during the twelfth week after treatment start while on protocol treatment. If 3 weekly chemotherapy regimen: can be completed during the third week of the fourth cycle of chemotherapy (D15-D21 of cycle 4).

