At 6 months	Can be completed at any time during the fifth and sixth month after date of randomization regardless of treatment or progression status.

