10.4 Statistical considerations

The primary HRQoL endpoint that is considered relevant for this study is **global QOL**. The following scales will be considered as secondary HRQoL endpoints: **role functioning, physical functioning, cognitive functioning, fatigue, diarrhea, and nausea and vomiting**. The other available scales will only be analyzed on an exploratory basis.

A difference of 10 points on the 100-point QLQ-C30 scale between the two arms will be considered as clinically relevant. The standard deviation of this scale is approximately 20 points. With the 1-sided alpha set at 10%, and a target difference of 10 points (effect size of 0.5), a minimum of 89 patients (in a 2:1 randomization) yields 80% power and 76 patients would yield 75% power. Therefore, this study is sufficiently powered to detect differences in HRQoL.

Data will be scored according to the algorithm described in the EORTC scoring manual. All scales and single items are scored on categorical scales and linearly converted to 0-100 scales.

Changes in HRQoL scores over time will be evaluated with summary statistics. The following two summary statistics will be used:

- ◆ During treatment: the change from baseline score to the worst score (ie minimum for functioning and global health scale; maximum for symptom scales) reported during treatment per patient will be compared.
- ◆ After treatment: the change from baseline score to the score at month 6.

Both summary statistics will be displayed via mean, median and standard deviation per treatment arm. Treatment differences will be displayed via mean differences and corresponding 90% confidence intervals. Treatment comparisons will be done via non-parametric logrank tests for the selected primary and secondary scales. Both statistical and clinical significance will be assessed.

Supportive analyses will be done by calculating the proportion of patients who experience a clinical significant deterioration (i.e. 10 point or more worsening) for both summary statistics.

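### HRQoL error control is misplaced: the between-arm compliance checks are tested at 0.01, while the 14 treatment comparisons have no stated error control

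*Combined protocol and SAP*

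**What the plan says.** On compliance, Section 10.3.2 states: "The compliance rate between the 2 arms will be compared at each time point using a chi-square test". It then adds that "a Bonferroni adjustment will be made by which each test will be performed at the 0.01 significance level". The table in Section 10.3.1 lists five time points: baseline, weeks 3, 6 and 12, and month 6.

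On the treatment comparison, Section 10.4 names global QoL as the primary HRQoL endpoint and six further scales as secondary; all other scales are exploratory. "The following two summary statistics will be used": the change to the worst score during treatment, and the change to month 6. "Treatment comparisons will be done via non-parametric logrank tests for the selected primary and secondary scales". No adjustment or testing order is given, and neither summary statistic is named as the main one for global QoL. The only alpha in the section is the one-sided 10% in the power statement. Treatment differences are shown with 90% confidence intervals.

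On the baseline form, Section 10.3 admits patients to the HRQoL assessment if they "complete the baseline HRQoL questionnaire before randomization". The table in Section 10.3.1 gives a wider window: "Can be completed before or on the day of start of protocol treatment but no earlier than 28 days before".

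**The concern.** The two sets of tests serve different purposes. The compliance test is a diagnostic. If it raises a false alarm, someone looks more closely at the missing forms. If it misses a real imbalance, the HRQoL comparison may be read as fair when one arm has lost more forms than the other. Section 10.4.1 itself treats missing data as a possible major source of bias. A Bonferroni level makes the costlier error more frequent.

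The treatment tests are where false positives matter. The introduction to Chapter 10 says that a PFS advantage will have to be weighed against treatment burden, so a chance HRQoL difference could affect how the trial is read. For these tests the plan states no error control, and even the single primary scale has two routes to significance.

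**Working it through.** **Inputs from the plan.** Section 8.1.1: "86 eligible patients who started their treatment (per protocol population) should be recruited (57 trabectedin, 29 control"). Five compliance time points (Section 10.3.1). Seven scales and two summary statistics (Section 10.4). One-sided 10%, SD 20 points and target difference 10 points (Section 10.4). Compliance rates and correlations between tests are not in the plan; they are assumptions, shown as ranges.

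**1. The plan's own level.** 0.05 / 5 time points = 0.01, which matches. The overall 0.05 is inferred; it is not written.

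**2. Power of the compliance test.** Exact enumeration over both binomial distributions, uncorrected chi-square test, 57 trabectedin against 29 control:

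| Assumed compliance, trabectedin vs control | Power at 0.01 | Power at 0.05 |
|---|---|---|
| 90% vs 70% | 44.8% | 64.4% |
| 85% vs 65% | 34.5% | 57.7% |
| 80% vs 60% | 29.3% | 52.2% |
| 65% vs 85% | 25.1% | 51.1% |

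Reversing the other two gaps gives 28.7% and 58.1% (70% vs 90%), and 22.8% and 47.4% (60% vs 80%). In every case a 20-point gap is missed more often than found at 0.01.

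For a 30-point gap at 0.01, power is 77% (90% vs 60%) and 69% (85% vs 55%); with the arms reversed it is 67% and 61%.

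The week 12 form is due only while on protocol treatment. If only progression-free patients are due a form, the plan's PFS-6 assumptions give 57 × 0.35^(12/26.1) ≈ 35 and 29 × 0.15^(12/26.1) ≈ 12. Power for 85% vs 65% is then 16.5% at 0.01 and 36.3% at 0.05.

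**3. False alarms in the compliance tests.** If independent: now 1 − 0.99^5 = 4.9%; at 0.05 each, 1 − 0.95^5 = 22.6%.

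**4. Treatment tests.** 7 × 2 = 14. The expected number of false positives at 10% is 14 × 0.10 = 1.4, whatever the correlation. The chance of at least one is 1 − 0.9^14 = 77% if independent. Simulation of equally correlated normal statistics gives:

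| Correlation | 14 tests | Global QoL, 2 tests |
|---|---|---|
| 0 | 77% | 19% |
| 0.3 | 57% | 18% |
| 0.5 | 46% | 17% |
| 0.7 | 35% | 15% |

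If each test were instead run at one-sided 5%, matching the 90% intervals, the 14-test figures at correlations 0, 0.5 and 0.7 would be 51%, 29% and 21%.

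**5. Power under possible remedies** (10-point difference, SD 20, 86 patients). One test at one-sided 10%: 82%. Global QoL on both statistics at 5% each: 71%. Bonferroni over all 14 (0.10 / 14 = 0.0071): 40%. Naming one test keeps the most power.

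**The case against.** Several points on the other side have force.

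- **The compliance test is not the only safeguard.** Section 10.3.2 has a twice-yearly review and a review trigger below 65%. Section 10.4.1 compares patients with and without data, models the compliance mechanism and plans imputation analyses, whatever the chi-square test shows. A reader might infer that unequal form loss would go unnoticed. The documents do not support that, and gaps of 30 points are usually flagged at full sample size. What remains is that none of these other steps is stated to compare arms. At 85% vs 65%, pooled compliance is (0.85 × 57 + 0.65 × 29) / 86 = 78%, so a pooled 65% trigger would not fire.
- **Sample size matters as well as the level.** In the four tabulated cases, 36–49% of 20-point gaps are still missed at 0.05. This stands: dropping Bonferroni helps but does not cure the problem.
- **The baseline test may look empty**, because Section 10.3 requires the form before randomization. But the Section 10.3.1 table allows completion up to treatment start, Chapter 6 allows 21 days between randomization and start, and the trial is open label. Baseline completion could therefore differ by arm, and the comparison should not be deleted on the present text.
- **The plan ranks its scales and sets 10 points as clinically relevant.** At 57:29 a one-sided 10% test is significant at 1.28 × 20 × √(1/57 + 1/29) ≈ 5.8 points. The chance that at least one of 14 null comparisons reaches 10 points is about 18% if independent and 8–11% at correlations 0.7 to 0.5. But Section 10.4 says both kinds of significance will be assessed; it does not require both.
- **Uncorrected secondary comparisons are defensible in a phase II trial**, provided that they are not presented as formal findings. The plan does not say so.

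**Conclusion.** The concern holds in limited form. The 0.01 level leaves the only stated between-arm compliance check with about 25–45% power for an assumed 20-point gap at full sample size, against 51–64% at 0.05. The 14 treatment comparisons have no stated error control: family-wise error is about 35–77% at one-sided 10% for correlations from 0.7 down to 0, and about 15–19% for global QoL alone.

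Two stronger inferences should not be drawn. One is that a chance HRQoL finding is likely: the figure falls below 50% at correlation 0.5 or more, which is plausible for scales completed by the same patients. The other is that the compliance tests use up alpha that the treatment tests needed: they are separate families, and each choice should be judged on its own.

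The results rest on assumed compliance rates and equal correlations, and on applying the power statement's alpha to every test. The matter concerns a secondary endpoint and leaves the PFS analysis untouched.

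**What to change.** **Section 10.3.2.** Drop the Bonferroni adjustment. Test each time point at 0.05 and report the between-arm compliance difference with a 95% confidence interval. Keep the baseline comparison unless Sections 10.3 and 10.3.1 are reconciled so that the baseline form must precede randomization. State that any flagged gap will be read alongside the Section 10.4.1 analyses.

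**Section 10.4.** Prespecify global QoL on one named summary statistic as the single formal HRQoL test, at one-sided 10%. Report the other 13 comparisons as estimates with confidence intervals and no claim of significance.

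**Cost.** A few sentences; no new patients, visits or data. The downside is more compliance false alarms (up to about 23% chance of at least one in five tests, if independent), and 13 comparisons lose formal-test status. This is a cheap improvement.

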10.4 Statistical considerations

The primary HRQoL endpoint that is considered relevant for this study is **global QOL**. The following scales will be considered as secondary HRQoL endpoints: **role functioning, physical functioning, cognitive functioning, fatigue, diarrhea, and nausea and vomiting**. The other available scales will only be analyzed on an exploratory basis.

A difference of 10 points on the 100-point QLQ-C30 scale between the two arms will be considered as clinically relevant. The standard deviation of this scale is approximately 20 points. With the 1-sided alpha set at 10%, and a target difference of 10 points (effect size of 0.5), a minimum of 89 patients (in a 2:1 randomization) yields 80% power and 76 patients would yield 75% power. Therefore, this study is sufficiently powered to detect differences in HRQoL.

Data will be scored according to the algorithm described in the EORTC scoring manual. All scales and single items are scored on categorical scales and linearly converted to 0-100 scales.

Changes in HRQoL scores over time will be evaluated with summary statistics. The following two summary statistics will be used:

- ◆ During treatment: the change from baseline score to the worst score (ie minimum for functioning and global health scale; maximum for symptom scales) reported during treatment per patient will be compared.
- ◆ After treatment: the change from baseline score to the score at month 6.

Both summary statistics will be displayed via mean, median and standard deviation per treatment arm. Treatment differences will be displayed via mean differences and corresponding 90% confidence intervals. Treatment comparisons will be done via non-parametric logrank tests for the selected primary and secondary scales. Both statistical and clinical significance will be assessed.

Supportive analyses will be done by calculating the proportion of patients who experience a clinical significant deterioration (i.e. 10 point or more worsening) for both summary statistics.

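### Section 10.4 powers HRQoL on the SD of the score but analyses unadjusted changes from baseline; the SD of change or the correlation should be stated, and baseline adjustment would add precision

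*Combined protocol and SAP*

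**What the plan says.** The power statement in section 10.4 starts from a relevance threshold: "A difference of 10 points on the 100-point QLQ-C30 scale between the two arms will be considered as clinically relevant". It then gives the spread: "The standard deviation of this scale is approximately 20 points". With a one-sided 10% level this is an effect size of 0.5, and the section states that "a minimum of 89 patients (in a 2:1 randomization) yields 80% power and 76 patients would yield 75% power". It concludes that HRQoL is adequately powered.

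The analysed variables are two changes per patient. One runs from baseline to the worst score during treatment. The other is defined as "After treatment: the change from baseline score to the score at month 6". On estimation the section says: "Treatment differences will be displayed via mean differences and corresponding 90% confidence intervals". The test is described as a non-parametric log-rank test. No covariate is named for the estimate or the test.

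Elsewhere, the Cox models for PFS (8.2.3.1) and OS (8.2.3.3) include the randomization factors other than institution, that is grade, age group and performance status (8.1.2). In the HRQoL chapter, prognostic variables enter only the modelling of compliance (10.4.1). Section 10.3 makes a completed baseline questionnaire a condition of HRQoL eligibility.

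**The concern.** The SD in the power sentence belongs to a different variable from the one compared. A change between two visits can vary more or less than a single score, depending on how strongly the visits correlate, and the plan does not give that correlation. The 80% and 75% figures therefore rest on an input that the reader cannot check.

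The comparison also leaves precision unused. A raw change subtracts the whole baseline score, although with imperfect correlation only part of a baseline difference persists to follow-up. With 29 controls, a chance baseline imbalance can carry into the treatment difference. Section 10 says any PFS gain must be weighed against treatment burden, so the precision of the HRQoL contrast matters to how the trial is read.

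**Working it through.** **Inputs.** From 10.4: difference 10, SD 20, one-sided 10% (z = 1.2816), 2:1 allocation, N = 89 and 76. From 8.1.1: 57 and 29 patients. Rho is not in the documents, so it is assumed and shown as a range. SDs are taken as equal at baseline and follow-up.

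**Reproducing the plan's figures.** Power = Φ(10 / (20·√(4.5/N)) − 1.2816) gives 82.7% at N = 89 and 78.0% at N = 76. Multiplying N by 3/π = 0.955, the efficiency of a rank-sum test under normality, gives 81.4% and 76.6%, each within two points of the stated 80% and 75%. So the plan's figures correspond to SD 20 with a rank test.

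**Month-6 change.** The SE factor is √(1/57 + 1/29) = 0.228.
- SD of change = 20·√(2(1 − rho)).
- Residual SD after baseline adjustment = 20·√(1 − rho²).
- Power = Φ(10 / (0.228·SD) − 1.2816).

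| rho (assumed) | SD of change | Power, raw change | Residual SD | Power, adjusted | Variance ratio (1 + rho)/2 |
|---|---|---|---|---|---|
| 0.3 | 23.7 | 71.6% | 19.1 | 84.5% | 0.65 |
| 0.4 | 21.9 | 76.4% | 18.3 | 86.7% | 0.70 |
| 0.5 | 20.0 | 81.9% | 17.3 | 89.4% | 0.75 |
| 0.7 | 15.5 | 93.9% | 14.3 | 96.3% | 0.85 |

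**Break-even.** For 80% power at N = 89 the SD of change may be at most 10·√(89·2/9) / (1.2816 + 0.8416) = 20.95, so rho must be at least 1 − 20.95²/800 = 0.45. With the rank-test factor the limits are 20.47 and 0.48. At the planned 86 patients the required rho is 0.47 (normal) or 0.49 (rank test).

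**Worst-score change.** The two-visit formula does not apply to a minimum over several visits. An illustrative simulation used three post-baseline scores, normal with SD 20 and equal correlation, and a 10-point difference in the summary statistic.

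| rho (assumed) | SD of change | Power, raw change | Residual SD, adjusted | Variance cut by adjustment |
|---|---|---|---|---|
| 0.3 | 21.0 | 79% | 15.5 | 45% |
| 0.5 | 17.7 | 88% | 14.5 | 32% |
| 0.7 | 13.6 | 97% | 12.3 | 19% |

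At rho 0.4 raw-change power was about 84%. The variance cut is 1 − (residual SD / SD of change)², for example 1 − (15.5/21.0)² = 0.45.

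**Baseline imbalance.** The baseline difference between arms has SE 20 × 0.228 = 4.6 points. With slope rho, an imbalance of that size moves the raw-change contrast by (1 − rho) × 4.6, which is 3.2 points at rho 0.3 and 1.4 at rho 0.7, against a threshold of 10.

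**Attrition.** The figures above assume that all 86 patients contribute. Section 10.3.2 expects numbers to fall and triggers a review below 65% compliance. At 65% of 86, about 56 patients, and SD 20, power is about 68% (normal approximation).

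**The case against.** A reader might infer that the HRQoL comparison is underpowered. The documents do not support that. They give no correlation, SD 20 is exactly right for a month-6 change at rho 0.5, and above that value power exceeds the stated figure. For the worst-score change, power is close to 80% even at rho 0.3. This objection stands: the power shortfall is a possibility that depends on rho, and it concerns mainly month 6.

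A reader might also infer that the unadjusted comparison is biased or ignores baseline. Subtracting baseline does use it, and under randomization the raw-change difference is unbiased. That too stands; the issue is precision and chance imbalance.

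Nor can adjustment be said always to win. Under 2:1 allocation, a main-effects ANCOVA can be less precise than the raw change if slopes differ by arm. With slopes 0.4 (trabectedin) and 1.2 (control), baseline variance 1 and residual variance 0.5, the scaled variances are 3.21 and 2.91. This needs a slope above 1, so it is unusual, but the fix should allow for it. The residual SD also stays at or below 20 only if the two SDs are equal: with a follow-up SD of 25 and rho 0.3 it is 25·√(1 − 0.09) = 23.8.

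Finally, the scales are bounded and diarrhea is a single item, so linearity is approximate. This bears on how the model is applied and does not remove the case for adjusting.

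**Conclusion.** The point holds as an unsupported power input and a missed gain in precision for a secondary endpoint of a phase II trial. It is not a demonstrated power failure and not a question of validity.

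For month 6, raw-change power ranges from about 72% to 94% for rho 0.3 to 0.7, against 85% to 96% with baseline adjustment, a variance reduction of 35% down to 15%. For the worst score the power shortfall is small, but adjustment still cuts variance by roughly 45% down to 20% over the same range. These sizes rest on assumed correlations, SD 20 at each visit, normal approximations, a common slope and full evaluability. The worst-score figures rest in addition on a simple three-visit model. No calculation was made for the added effect of adjusting for grade, age group and performance status.

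**What to change.** In section 10.4:
- Estimate the treatment difference for each summary statistic by ANCOVA of the follow-up score (worst or month 6) on arm, baseline score, grade, age group and performance status. Because allocation is 2:1, use robust standard errors or add an arm-by-centred-baseline term.
- Report the adjusted mean difference with its 90% CI.
- Name rank ANCOVA as the non-parametric test for bounded or single-item scales. This would also replace the log-rank label, which is not the usual name for a test of change scores.
- Restate the power sentence for the variable analysed, giving the SD of change or residual SD, the assumed correlation, and the number expected to be evaluable. The planned 86 is already below the 89 quoted for 80% power.

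The cost is wording and one model per scale and summary statistic, on data already collected. The downside is slightly more analysis work and only approximate linearity on bounded scales.

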10.1 Objective

The study hypothesis is that trabectedin chemotherapy will result in a PFS-6 of 35% compared to 15% in the control arm. In the present study, HRQoL is an important secondary endpoint. The main objective of HRQoL assessment within this trial is to determine the impact of trabectedin on **seven chosen domains being primarily global QoL, with role functioning, physical functioning, cognitive functioning, fatigue, diarrhea, and nausea and vomiting as secondary key issues**. It is expected that these were likely to be most affected in patients undergoing trabectedin chemotherapy. The Ho hypothesis will be tested to show that there is no difference between patients in both arms during and after treatment for the selected scales. A secondary objective is to evaluate the effect of the treatment on the remaining symptoms and functioning scales as treatment-related side effects may have a (temporary) negative influence on the health related domains of HRQoL of these patients.

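### Section 10.4 names a logrank test for HRQoL change scores whose sample size was computed for the rank-sum test, and its power claim is not limited to a comparison

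*Combined protocol and SAP*

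**What the plan says.** Section 10.4 makes global QoL the primary HRQoL scale and six further scales secondary. Each is summarised by two numbers per patient: the change from baseline to the worst on-treatment score, and the change from baseline to month 6. Results are shown as means, medians, standard deviations and mean differences with 90% confidence intervals. The test is set in one sentence: "Treatment comparisons will be done via non-parametric logrank tests for the selected primary and secondary scales". The supportive analysis is a proportion of patients who deteriorate, not a time to deterioration.

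The sizing in the same section uses a one-sided alpha of 10% and a 10-point difference. On spread it says: "The standard deviation of this scale is approximately 20 points". From this, "a minimum of 89 patients (in a 2:1 randomization) yields 80% power and 76 patients would yield 75% power". It concludes: "Therefore, this study is sufficiently powered to detect differences in HRQoL".

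The null hypothesis in section 10.1 is that "there is no difference between patients in both arms during and after treatment for the selected scales". Section 10.3.2 expects attrition: "Available patient numbers will diminish during the trial due to progression, death, or loss to follow-up". Section 8.1.1 plans 86 eligible patients who start treatment (57 and 29).

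**The concern.** A logrank test compares times to an event. Section 10.4 has a signed change score with no censoring. Software will still run a logrank test on such values if the score is entered as a time and every patient is counted as an event, so nothing would flag the mismatch. The result then depends on whether scores are ordered from worst to best or the reverse. The plan says which end of each scale is worse, but not how a logrank test should order the changes. An analyst following the text would run a test other than the one that was powered, and would make an unstated choice in an open-label trial.

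The second issue is how a null result would be read. The hypothesis covers the periods during and after treatment, but the power conclusion names neither. A non-significant month-6 result could be read against a general claim of adequate power, although that comparison is expected to have fewer patients.

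**Working it through.** **Inputs.** From section 10.4: one-sided alpha 10%, difference 10 points, SD 20 (effect size 0.5), 2:1 allocation, 89 patients for 80% power and 76 for 75%. From section 8.1.1: 86 patients (57 and 29). From sections 10.3.2 and 10.4.1: compliance levels of 65% and 50%.

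**Reproducing 89 and 76.** The Noether formula for the rank-sum test is N = (z_0.90 + z_power)² / [12 c(1−c)(p − 0.5)²], with c = 2/3 and p = Φ(0.5/√2) = 0.6382. The denominator is 12 × 2/9 × 0.1382² = 0.0509.

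- 80% power: (1.2816 + 0.8416)² / 0.0509 = 88.56, so 89.
- 75% power: (1.2816 + 0.6745)² / 0.0509 = 75.16, so 76.

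Both match exactly. The alternatives tried do not:

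| Method | 80% power | 75% power |
|---|---|---|
| Stated in section 10.4 | 89 | 76 |
| Rank-sum (Noether) | 88.56 | 75.16 |
| Normal approximation for means | 81.1 | 68.9 |
| t-test | 82 | 70 |
| Normal size / 0.955 (relative efficiency) | 85.0 | 72.1 |
| Normal size / 0.864 (relative efficiency) | 93.9 | 79.7 |
| Normal approximation, two-sided | 114 | 99 |

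No logrank size can be computed, because section 10.4 gives no hazard ratio, event count or censoring rule.

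**Effect of following the text literally.** Simulation: 57 and 29 patients, normal change scores with SD 20, one-sided 10%, 20,000 trials per setting. Scores are continuous, or rounded to steps of 8.33 or 16.67 points (the steps are assumed). Entries are in that order.

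| Rejection rate (%) | No difference | 10-point difference |
|---|---|---|
| Rank-sum | 10.1 / 10.2 / 9.9 | 80.3 / 80.5 / 79.0 |
| Logrank, worst score first | 11.2 / 10.7 / 10.3 | 77.3 / 78.7 / 78.5 |
| Logrank, best score first | 9.5 / 9.9 / 9.6 | 75.2 / 77.3 / 77.6 |

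The power loss runs from 79.0 − 78.5 = 0.5 points to 80.3 − 75.2 = 5.1 points. Logrank and rank-sum disagree on significance in 7–13% of trials with a 10-point difference and in 4–7% with none. For scale, the t-test and rank-sum test disagree in about 5% and 3% of trials with continuous scores. Part of the disagreement is therefore what any change of test produces.

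**Power by number evaluable.** Power = Φ(√(0.0509 N) − 1.2816), at effect size 0.5:

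| Evaluable N | Power |
|---|---|
| 89 | 80.1% |
| 86 (planned) | 79.1% |
| 76 | 75.3% |
| 56 (65% of 86 = 55.9) | 66% |
| 43 (50% of 86) | 58% |

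**The case against.** The strongest reply is that the intent is plain. The data are change scores, the plan calls the test non-parametric, and the sample size gives the answer away. No competent analyst would fit a survival test, and if one did, little would change. This largely stands, and it is why the point is modest. It does not make the text right: this is the prespecified test for the primary and six secondary HRQoL scales, and correcting it is free.

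On power, the plan is not silent about attrition. It gives a second power point at 76 patients, triggers a review if compliance falls below 65% at any assessment, makes the analysis exploratory below 50% overall, and plans dropout analyses and imputation. The month-6 form is also collected after progression: "Can be completed at any time during the fifth and sixth month after date of randomization regardless of treatment or progression status". HRQoL is "evaluated in a longitudinal design in all patients entered in this study", so the number entered may exceed 86. All of this is fair. Those rules govern compliance and missing data, however, and none qualifies the power conclusion.

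Three stronger readings are tempting, and the documents do not support them.

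- **That the HRQoL comparison would be invalid.** Type I error stays at 9.5–11.2% against a nominal 10%.
- **That month-6 power can be put at a definite low figure from survival.** The documents give no expected month-6 number. The 7 to 13 month median survival in section 1.1 comes from small case series and is not a planning assumption of this trial.
- **That 86 against a minimum of 89 is itself a serious shortfall.** It is 79% against 80%.

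**Conclusion.** Wrong as written, with a modest effect. The test named in section 10.4 fits neither the variables nor the sample size, which is exactly that of a rank-sum test. Applied literally, it costs about 1 to 5 points of power, roughly keeps the type I error and changes some significance calls. These simulated figures assume normal, unbounded scores, whereas the real scales run from 0 to 100. They also assume a one-sided 10% decision level, which section 10.4 states for the power calculation but not for the tests themselves.

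The power conclusion is a secondary point. It is too general, because power depends on the number evaluable in each comparison and the plan itself expects that number to fall. The 66% and 58% are examples. They read the two compliance levels as shares of 86, and they assume an effect size of 0.5. The SD of 20 is stated for the scale, and none is given for a change score, so power for the change scores could be higher or lower.

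The primary PFS analysis, the HRQoL mean differences, the 90% confidence intervals and the deterioration proportions do not depend on either point.

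**What to change.** Two edits in section 10.4:

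1. In the sentence that sets the treatment comparisons, replace the logrank wording with: *Wilcoxon rank-sum (Mann-Whitney) tests*. The figures 89 and 76 stand.
2. Replace the concluding power sentence with: *These figures apply to the number of patients evaluable for the given comparison and assume an effect size of 0.5: about 79% power with 86 evaluable patients and 75% with 76. The month-6 comparison is expected to have fewer evaluable patients and therefore lower power (for example, about 66% with 56 patients, 65% of 86, and 58% with 43, 50% of 86, the compliance levels named in 10.3.2 and 10.4.1).*

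The new text should contain no survival-based patient numbers and no change-score SD, because the documents support neither. The cost is one test name and one sentence, with a slightly less favourable power statement. No new data, patients or analyses are needed. Both edits should be made before the HRQoL analysis.
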